### 2.2.4 Potential risks and benefits

As previously noted, clinical proof of concept for BIVV009 was achieved in a Phase 1b study, which demonstrated immediate cessation of hemolysis and rapid correction of anemia during short-term treatment of patients with CAgD.

The human safety risk from off-target effects of mAb therapeutics is generally considered to be low, and in this regard BIVV009 is no exception. The human safety risk from short-term inhibition of the complement system also appears to be low, based upon the experience with five approved products in this therapeutic class. Long-term, complement inhibition may increase the risk of infection with encapsulated bacteria, as reflected in the product label for eculizumab (Soliris), an inhibitor of the terminal portion of the complement system. However, to provide

optimal protection against infections with encapsulated bacteria, the design of this study includes an appropriate program of prophylactic vaccinations.

The risks associated with long-term inhibition of the proximal portion of the CP are presently unknown. Theoretically, it could increase the risk of SLE or circulating immune complexes (CIC) disease due to the role of the C1 complex in immune complex clearance, as observed in patients with congenital deficiencies of C1 complex components (C1q, C1s, and C1r). However, pharmacologic inhibition of C1s differs from congenital deficiency of the C1 complex because: 1) congenital C1 complex component deficiency are commonly not single gene mutations but typically are associated with second mutations in other immune system genes; 2) pharmacologic inhibition of C1s enzymatic function in the C1 complex leaves intact the non-enzymatic function of C1q, which is important for the opsonization and phagocytic removal of apoptotic cells which protects against autoimmunity; and 3) the phenotype associated with life-long, often total absence of C1 complex structure and function is unlikely to be reproduced by pharmacologic antagonism of C1 enzymatic function in fully developed adults. Nevertheless, standard clinical biomarkers related to SLE (eg, antibodies to double-stranded DNA [dsDNA]) have been incorporated into the study design as safety surveillance measures.

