4.7.2 Adverse events

General common rules for adverse events

AEs will be classified using the MedDRA system organ classes and preferred terms. MedDRA version 20.1 or higher will be used throughout the study.

In general, AEs will be analyzed based on *incidence*, defined as the proportion of subjects who had at least one occurrence of an event out of the number of subjects in the Safety Analysis Set. An adverse event listing will be provided and will include all adverse events reported with the onset and resolution study days relative to Day 0 (Study Day 1).

All summary table analyses will only include treatment-emergent adverse events unless noted otherwise.

Unless specified otherwise, system organ classes (SOCs) and preferred terms (PTs) within each SOC will be presented alphabetically. For the purpose of summarization, a subject is counted once in a SOC or preferred term if the subject reported one or more events in that SOC or preferred term. Unless specified otherwise, percentages will be based on the number of subjects in the Safety Analysis Set.

Overall Summary of Adverse Events

An overall summary of TEAEs will be provided which tabulates the number and percentage of subjects who experienced a TEAE, related TEAE, TEAE grade 3 or higher, TEAE infection of grade 3 or higher, TEAE thromboembolic event, TEAE within 24 hours of the start of infusion, TESAE, related TESAE, and TESAE infection; the number and percentage of subjects who discontinued treatment and/or the study due to a TEAE and the number and percentage of subjects who died on-study.

Treatment-emergent Adverse Events

The incidence of TEAEs will be summarized by SOC and preferred term.

Adverse Events in Descending Order of Incidence

A table will be provided which displays TEAE preferred terms in descending order of incidence. Only preferred terms will be included in this table (ie, the display will not include SOCs).

A similar table will be provided for Grade 3 or higher TEAEs. AEs for which the assessment of severity is missing will be included in this table in the TEAE Grade 3 or higher category.

Severity of Adverse Events

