4 STATISTICAL ANALYSES

Part B is an open-label study with no blinding or randomization. No formal statistical hypotheses will be tested. Analyses of efficacy endpoints will be primarily descriptive.

Statistical analysis will be performed by Sanofi, using SAS 9.4 or higher and, where appropriate, additional validated software.

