4.7.2 Adverse events

General common rules for adverse events

AEs will be classified using the MedDRA system organ classes and preferred terms. MedDRA version 23.0 or higher will be used throughout the study.

In general, AEs will be analyzed based on *incidence*, defined as the proportion of subjects who had at least one occurrence of an event out of the number of subjects in the Safety Analysis Set.

All summary tables and listings will only include treatment-emergent adverse events in Part B unless noted otherwise.

Unless specified otherwise, system organ classes and preferred terms within each SOC will be presented alphabetically. For the purpose of summarization, a subject is counted once in a SOC or preferred term if the subject reported one or more events in that SOC or preferred term. Unless specified otherwise, percentages will be based on the number of subjects in the Safety Analysis Set.

Overall Summary of Adverse Events

An overall summary of TEAEs will be provided which tabulates the number and percentage of subjects who experienced a TEAE, related TEAE, treatment-emergent SAE, treatment-emergent related SAE, treatment-emergent Grade 3 or higher AE, treatment-emergent infections of Grade 3 or higher severity, TEAE thromboembolic event, TEAE autoimmune event, TEAE potential hypersensitivity event, and TEAEs within 24 hours after the start of infusion; TEAEs within 24 hours after the start of home infusion of BIVV009 and TEAEs within 24 hours after the start of undiluted infusion of BIVV009; the number and percentage of subjects who discontinued treatment and/or the study due to an AE; and the number and percentage of subjects who died. In addition, the number of TEAEs, TESAEs, TEAE thromboembolic events and TEAEs within 24 hours after the start of infusion will be presented.

Treatment-emergent Adverse Events

The incidence of TEAEs will be summarized by SOC and preferred term.

Adverse Events in Descending Order of Incidence

Tables will be provided which display TEAE and TESAE preferred terms in descending order of incidence. Only preferred terms will be included in these tables (ie, the display will not include SOCs).

A similar table will be provided for Grade 3 or higher TEAEs. AEs for which the assessment of severity is missing will be included in this table.

Severity of Adverse Events

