All AEs within 24 hours after the start of site infusion are captured in the eCRF. Incidence of AEs within 24 hours after the start of site infusion will be summarized by SOC and preferred term.

AEs within 24 Hours after the Start of Home Infusion

All AEs within 24 hours after the start of home infusion are captured in the eCRF. Incidence of AEs within 24 hours after the start of home infusion will be summarized by SOC and preferred term. AEs within 24 hours after the start of home infusion will be flagged on the listing of adverse events.

AEs within 24 Hours after the Start of Undiluted Infusion

All AEs within 24 hours after the start of undiluted infusion are captured in the eCRF. Incidence of AEs within 24 hours after the start of undiluted infusion will be summarized by SOC and preferred term. AEs within 24 hours after the start of undiluted infusion will be flagged in the listing of adverse events.

Infections and Infections of \geq Grade 3 Severity

Infections will be captured based on MedDRA SOC of “infections and infestations.” Incidence of infections of Grade 3 or higher will be summarized by preferred term. Listings of all infections, infections of Grade 3 or higher and serious infections will be provided.

Autoimmune Events

Treatment-emergent autoimmune events will be adjudicated and flagged on the Listing of adverse events.

Hypersensitivity Events

Treatment-emergent hypersensitivity events will be adjudicated and flagged on the Listing of adverse events.

Anti-drug Antibody

Subjects will be evaluated for anti-drug antibodies at Baseline and at the ET/EOS/Safety Follow-up visits in Part B. Subjects with negative or positive anti-drug antibodies at baseline and post baseline, as well as the incidence and prevalence will be summarized for the Combined Study Period by dose cohort in Part B (ie, 6.5 g and 7.5 g) and Total. A listing will be provided for subjects with negative or positive anti-drug antibodies along with the associated titer if available. If applicable, TEAEs for those subjects will be included in the same listing.

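### Adjudicated, grouped autoimmune and hypersensitivity event counts are specified only for open-label Part B and should be added, by arm, to placebo-controlled Part A

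*SAP*

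**What the plan says.** **Part B SAP, 4.7.2.** Two categories have their own entries among the events of special interest: "Treatment-emergent autoimmune events will be adjudicated and flagged on the Listing of adverse events" and "Treatment-emergent hypersensitivity events will be adjudicated and flagged on the Listing of adverse events". Both are also counted, as number and percentage of subjects, in the overall summary: "TEAE autoimmune event, TEAE potential hypersensitivity event". The scope is stated as "All summary tables and listings will only include treatment-emergent adverse events in Part B unless noted otherwise". Section 4 describes the setting: "Part B is an open-label study with no blinding or randomization".

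**Part A SAP, 4.7.2.** The overall summary lists, among others, "TEAE infection of grade 3 or higher, TEAE thromboembolic event, TEAE within 24 hours of the start of infusion", but has no autoimmune or hypersensitivity category. The events of special interest are AEs within 24 hours of infusion, infections, hemolytic breakthrough and anti-drug antibodies. Section 4.7 presents safety by treatment arm, descriptively and without testing. Section 4.7.2 tabulates all TEAEs by system organ class and preferred term. Section 4.7.3.1 summarises the SLE panel, including conversion from negative to positive.

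**Protocol.** Section 2.2.2 names autoimmune disease and bacterial infection as the hypothetical mechanism-related risks of C1s inhibition. Section 2.2.4 says of long-term inhibition: "Theoretically, it could increase the risk of SLE or circulating immune complexes (CIC) disease".

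**The concern.** Autoimmune disease is a risk the protocol itself derives from the drug's mechanism. Hypersensitivity is not on that list, but the protocol takes it seriously: it is a ground for withdrawal (5.3), has its own testing section (6.3.8), and is reported as an SAE when Grade 3 or higher (6.7.1.2). The sponsor thought both categories worth adjudicating and counting, yet specified this only where there is no comparator.

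In Part A, reported terms would be spread over preferred terms and organ classes. Subjects are counted once within each term or class, so those tables do not show how many patients per arm had any autoimmune event or any hypersensitivity event. At stake is the one setting where classification could be blinded and set against concurrent placebo.

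The documents give no reason for the difference. Part A SAP Version 2 (02-Oct-2020) is later than Part B SAP 1.0 (20-Jul-2020). The categories therefore already existed when the Part A plan was reopened, and the only change recorded in that version is the primary test.

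**Working it through.** **1. The two plans side by side**

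| Item | Part A SAP | Part B SAP |
|---|---|---|
| Comparator | Randomised placebo, output by arm | None, open label |
| Autoimmune TEAEs adjudicated | No | Yes |
| Hypersensitivity TEAEs adjudicated | No | Yes |
| Rows in the overall TEAE summary | Neither | Both |
| All TEAEs by organ class and preferred term | Yes | Yes |
| AEs within 24 hours of infusion | Yes | Yes |
| SLE panel with conversion | Yes | Yes |

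Only the adjudication and the grouped count differ.

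**2. Can Part B output reach back into Part A?** By default its AE tables and listings cover Part B TEAEs only. A Combined Study Period is defined (Part B SAP 4.1) for a subset of analyses. Exposure, total dose and anti-drug antibodies are assigned to it (4.7.1, 4.7.1.1, 4.7.2); autoimmune and hypersensitivity events are not.

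**3. Who reaches Part B?** Protocol 5.3 lists clinical signs of SLE or another immune complex disease, and hypersensitivity or allergic reaction to study drug, as grounds for withdrawal. Part B SAP section 2 says patients who withdraw from the study in Part A cannot enter Part B. A patient withdrawn in Part A for either kind of event is therefore never in the adjudicated population. For the arm randomised to BIVV009, first exposure is on Day 0, outside the adjudicated period. Former placebo patients have their first exposure at Week 26, without a control group.

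**4. Share of BIVV009 time without adjudication, arm randomised to BIVV009.** Inputs: 26 weeks in Part A; Part B dosing of 1 to 2 years, taken as 52 to 104 weeks (Protocol 4.4).
- Part B of 1 year: 26 / (26 + 52) = 33%.
- Part B of 2 years: 26 / (26 + 104) = 20%.

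In the placebo arm, no placebo time is adjudicated.

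**5. What a by-arm table could show.** The plan gives no figure for these events. Its one design figure is 87% power with 20 per group, 85% versus 35%, two-sided 5% (Protocol 7.10). Exact enumeration with Fisher's test gives 87.5%, so it reproduces. It matters here only because it fixes the arm size at 20.
- No events in 20, two-sided 95% upper limit: 1 − 0.025^(1/20) = 16.8%. One-sided 95%: 1 − 0.05^(1/20) = 13.9%.
- Chance of at least one event in 20 at true rate r, 1 − (1 − r)^20: 64% at r = 5%, 88% at 10%, 99% at 20%.
- Fisher's test against 0/20: 4/20 gives p = 0.106 and 5/20 gives p = 0.047. Power against a 0% placebo rate is about 4% at a 10% rate and 37% at 20%.

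The event rates are assumptions; the documents give none.

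**The case against.** **Part A follows the protocol.** Protocol 7.8.2 asks for specific tables on hemolytic breakthrough, Grade 3 or higher infections and thrombotic events, and 4.3.5 lists no autoimmune-event endpoint. The extra Part B categories suit its long-term safety objective. This stands: the point is an improvement, not a breach of the protocol.

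**The protocol's chosen surveillance for autoimmunity is SLE serology.** Part A compares it by arm, from samples at screening and at Day 182 before the crossover dose. This also stands, but serology is not a count of clinical events. Likewise, the 24-hour AE table is unadjudicated and does not cover reactions that start later.

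**The gain is small.** With about 20 per arm and no safety testing planned, the table cannot establish or exclude a difference of moderate size. That is correct. The benefit is consistent, blinded classification, not power.

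**No written rules exist to carry over.** The Part B SAP gives neither a term list nor an adjudicator for these two categories; internal medical staff are named only for thromboembolic events. This stands and adds a task to the fix. That existing staff could do the work is an assumption, although Part A already plans medical review of thromboembolic AEs (Part A SAP 4.5.2).

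**Conclusion.** The asymmetry is real and unexplained, and it should be corrected. Part A lacks an adjudicated, grouped, by-arm count of autoimmune and hypersensitivity events. Part B counts cannot replace it, because they have no control, miss first exposure in the arm randomised to BIVV009, and come from a population selected against these events. How strong that selection is depends on how many patients withdraw in Part A for these reasons, which the documents do not give. The primary efficacy analysis, sample size and alpha are unaffected.

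Four stronger readings are tempting, but the documents do not support them:
- *That the autoimmune risk gets no randomised comparison.* The SLE panel and all TEAEs are presented by randomised arm.
- *That ascertainment starts at Week 26.* AEs are recorded from consent (Protocol 6.7) and MedDRA-coded in Part A; only adjudication is missing before Week 26. The 20% to 33% is time without adjudication, not time without event collection.
- *That a combined-period rate will mislead.* No combined-period summary of these events is planned.
- *That both categories are named mechanism-related risks.* Only autoimmune disease is. The other named risk, infection, is already a special-interest item by arm in Part A.

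**What to change.** Before the Part A unblinding:

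1. Write down the autoimmune and hypersensitivity classification used for Part B (term list, decision rule, who decides) and cite it in both SAPs.
2. Apply it to all Part A TEAEs with reviewers blinded to arm. Part A SAP 1.1 keeps sponsor personnel, other than those supplying drug, blinded until the Part A analysis, so this is feasible. The unblinded team members allowed by Protocol 6.2.5 should not take part.
3. Add an autoimmune row and a potential-hypersensitivity row, by arm, to the Part A overall TEAE summary, and flag the events in the Part A AE listing.
4. Label the rows as descriptive and show exact confidence intervals, so that zero counts are not read as absence of risk.

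The cost is a short written rule, a blinded medical review of AEs in about 40 patients, two table rows and a listing flag. No new data are collected.

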Chemistry		Hematology	
Liver		White blood cells	Low and High
ALT/SGPT	High	Lymphocytes	Low and High
AST/SGOT	High	Neutrophils	Low and High
Total bilirubin	High	Monocytes	Low and High
GGT	High	Eosinophils	Low and High
Renal		Basophils	Low and High
Blood urea nitrogen	High	Red blood cells	Low and High
Creatinine	High	Hemoglobin	Low and High
Electrolytes		Hematocrit	Low and High
Sodium	Low and High	Platelets	Low and High
Potassium	Low and High		
Chloride	Low and High		
Other			
Glucose	Low and High		
Total protein	Low and High		

Potentially Clinically Significant Laboratory Abnormalities

Abnormal laboratory values (excluding LDH, haptoglobin, and reticulocytes) will also be evaluated by determining the number and percentage of subjects with at least one potentially clinically significant laboratory abnormality over the course of Part B of the study that also represents a worsening from baseline. The potentially clinically significant levels are based on Grade 2 or higher thresholds from the CTCAE v4.03 where possible, or are defined by Sanofi's safety group. Subjects who have a post baseline laboratory value that meets the criteria for being potentially clinically significant but do not have a baseline value will be included in the numerator for determining the percentage of subjects with an abnormality. The laboratory tests and thresholds for determining PCSAs are provided in [Table 5](#).

Table 5 - Thresholds for potentially clinically significant laboratory abnormalities

Laboratory Test	Threshold	Laboratory Test	Threshold
Chemistry		Hematology	
ALT (U/L)	>= 3 x ULN	Hematocrit (%)	<= 30% >= 60%
Albumin (g/dL)	<= 2.5 g/dL	Hemoglobin (g/L)	<= 100 g/L >= 190 g/L
Alkaline Phosphatase (U/L)	> 2.5 x ULN	MCV (fL)	>= 1.2 x ULN <= 0.8 x LLN
AST (U/L)	>= 3 x ULN	Platelet count (10 ⁹ /L)	<= 75 x 10 ⁹ /L >= 700 x 10 ⁹ /L
Blood urea nitrogen (mmol/L)	>= 10.7 mmol/L	WBC (10 ⁹ /L)	<3 x 10 ⁹ /L >= 16 x 10 ⁹ /L
Chloride (mmol/L)	<= 90 mmol/L >= 118 mmol/L	Basophils (10 ⁹ /L)	> 1.6 x 10 ⁹ /L
Creatinine (umol/L)	> 1.5 x ULN	Eosinophils (10 ⁹ /L)	> 1.6 x 10 ⁹ /L
GGT (U/L)	> 2.5 x ULN	Lymphocytes (10 ⁹ /L)	> 0.8 x 10 ⁹ /L
Glucose (mmol/L)	<3 mmol/L > 8.9 mmol/L	Monocytes (10 ⁹ /L)	< 2.5 x 10 ⁹ /L
Potassium (mmol/L)	<= 3 mmol/L >= 6 mmol/L	Neutrophils (10 ⁹ /L)	> 1.5 x 10 ⁹ /L
Sodium (mmol/L)	<= 126 mmol/L >= 156 mmol/L		
Total bilirubin (umol/L)	> 1.5 x ULN		
Direct bilirubin (umol/L)	> 1.5 x ULN		
Total protein (g/L)	<= 45 g/L >= 100 g/L		

All data collected during Part B, including data collected from unscheduled visits, will be included in this analysis.

Systemic Lupus Erythematosus (SLE) Panel

SLE panel will be summarized with descriptive statistics. The number of subjects with all negative or all missing values for all SLE panel parameters prior to receiving study drug and the number of subjects with at least one positive value for at least one SLE panel parameter prior to receiving study drug will be summarized. Further, among subjects who have all negative or all missing values for all SLE parameters prior to receiving study drug and have at least one post-baseline value for at least one parameter, the number of subjects who test negative at all post-baseline assessments for all SLE parameters, and the number of subjects who test positive at any post-baseline assessment for at least one SLE parameter will be summarized.

Similar summaries will be generated for individual SLE parameters. In addition, for a given SLE parameter, among subjects who have at least one positive or all missing values prior to receiving study drug and have at least one post-baseline for this parameter, the number of subjects who test positive at all post-baseline assessments, and the number of subjects who test negative at any post-baseline assessment will be summarized.

Parameters in the SLE panel include Antinuclear antibody (ANA), multiplex with dsDNA, Anti-La/SSB antibody (SS-B), Anti-ribonucleoprotein antibody (RNP), Anti-Smith antibody (Sm), Anti-Ro/SSA antibody (SS A), Anti-scleroderma antibody (Scl-70), Anti-Chromatin antibody, Anti-Jo-1 antibody, Anti-Centromere B antibody, Circulating immune complexes (CIC).

ECG and Vital Signs

The proportion of subjects with specific clinical interpretations (Normal; Abnormal, not an AE; Abnormal, AE) will be summarized by visit, through the end of Part B.

The proportion of subjects with a shift in clinical interpretation from baseline will be summarized. All data collected during Part B, including data collected from unscheduled visits, will be included in this analysis.

Vital signs

Vital signs (systolic and diastolic blood pressure, pulse, respiratory rate, and temperature) will be summarized by visit, through the end of Part B, for the observed values and change from baseline using descriptive statistics for the Safety Analysis Set.

The number and percentage of subjects with potentially clinically relevant post-baseline abnormalities will be presented. All data collected during Part B, including data collected from unscheduled visits, will be included in this analysis. The criteria for potentially clinically relevant post-baseline abnormalities are shown below in [Table 6](#).

Table 6 - Criteria to determine clinically relevant abnormalities in vital signs

Vital Sign	Criteria for Abnormalities
Temperature	>38°C and an increase from pre-dosing of at least 1°C
Pulse	>120 beats per minute post-baseline or an increase from pre-dosing of more than 20 beats per minute; <50 beats per minute post-baseline or a decrease from pre-dosing of more than 20 beats per minute
Systolic Blood Pressure	>180 mmHg post-baseline or an increase from pre-dosing of more than 40 mmHg; <90 mmHg post-baseline or a decrease from pre-dosing of more than 30 mmHg
Diastolic Blood Pressure	>105 mmHg post-baseline or an increase from pre-dosing of more than 30 mmHg; <50 mmHg post-baseline, or a decrease from pre-dosing of more than 20 mmHg
Respiratory Rate	>35 breaths per minute post-baseline; <10 breaths per minute post-baseline

